13.4. Reporting Adverse Events

The Investigator will notify the Sponsor of an adverse event by e-mail, facsimile, or telephone as soon as possible and no later than 24 hours from discovery for any serious /significant adverse events, and 2 days from discovery for any non-significant adverse event. In addition, a written report will be submitted by the Principal Investigator to the IEC/IRB according to their requirements (Section 13.4.2). The report will comment whether or not the adverse event was considered to be related to the test article, study treatment or study procedures.

13.4.1. Reporting Adverse Events to Sponsor

Serious/Significant Adverse Events

The Investigator will inform the sponsor of all serious/significant adverse events occurring during the study period as soon as possible by e-mail, fax, or telephone, but no later than 24 hours following discovery of the event. The Investigator is obligated to pursue and obtain information requested by the Sponsor in addition to that information reported on the eCRF. All subjects experiencing a serious/significant adverse event must be followed up and all outcomes must be reported.

When medically necessary, the Investigator may break the randomization code to determine the identity of the treatment that the subject received. The Sponsor and study monitor should be notified prior to unmasking the test articles.

In the event of a serious/significant adverse event, the Investigator must:

- Notify the Sponsor immediately
- Obtain and maintain in the subject's records all pertinent medical information and medical judgment for colleagues who assisted in the treatment and follow-up of the subject
- Provide the Sponsor with a complete case history which includes a statement as to whether the event was or was not related to the use of the test article
- Notify the IEC/IRB as required by the IEC/IRB reporting procedure according to national regulations

Unanticipated (Serious) Adverse Device Effect (UADE)

In the event of an Unanticipated (Serious) Adverse Device Effect (UADE), the Investigator will submit a report of the UADE to the Sponsor and IEC/IRB as soon as possible, but no later than 24 hours after the Investigator first learns of the effect. This report is in addition to the immediate notification mentioned above.

The Sponsor must conduct an evaluation of the UADE and must report the results of the evaluation to FDA, the IEC/IRB and participating Investigators within 10 working days after the Sponsor first receives notification of the effect.

Non-Serious Adverse Events

All non-serious adverse events, including non-serious adverse device effects, will be reported to the sponsor by the Investigator no later than 2 days from discovery.

13.4.2. Reporting Adverse Events to the Responsible IEC/IRB and Health Authorities

Adverse events that meet the IEC/IRB requirements for reporting must be reported within the IEC/IRB's written guidelines. Each clinical site will refer to and follow any guidelines set forth by their Approving IEC/IRB. Each clinical site will refer to and follow any guidelines set forth by their local governing Health Authorities.

The Sponsor will report applicable Adverse Events to the local health authorities according the written guidelines, including reporting timelines.

13.4.3. Event of Special Interest

None.

13.5. Reporting of Pregnancy

Subjects reporting pregnancy (by self-report) during the course of the study will be discontinued after the event is recorded as an Adverse Event. Once discontinued, pregnant participants and their fetuses will not be monitored for study related purposes. At the Investigator's discretion, the study participant may be followed by the Investigator through

delivery. However, this data will not be collected as part of the clinical study database. Pregnant participants are not discontinued from contact lens or solution related studies for safety concerns, but due to general concerns relating to pregnancy and contact lens use. Specifically, pregnant women are discontinued due to fluctuations in refractive error and/or visual acuity that occur secondary to systemic hormonal changes, and not due to unforeseen health risks to the mother or fetus.

14. STATISTICAL METHODS

14.1. General Considerations

Statistical Analysis will be undertaken by the sponsor or under the authority of the sponsor. A general description of the statistical methods to be implemented in this clinical trial is outlined below.

All data summaries and statistical analyses will be performed using the SAS software Version 9.4 or higher (SAS Institute, Cary, NC). Throughout the analysis of data, the results for each subject/eye will be used when available for summarization and statistical analysis. Unscheduled visits will be summarized separately.

Summary tables (descriptive statistics and/or frequency tables) will be provided for all baseline variables, efficacy variables and safety variables as appropriate. Continuous variables will be summarized with descriptive statistics (n, mean, standard deviation [SD], median, minimum and maximum). Frequency count and percentage of subjects or eyes within each category will be provided for categorical data.

Summaries will be presented by study solution, by lens type and across all lens types.

14.2. Sample Size Justification

This is a pilot study and the sample size was not based on any empirical power calculation. The collected data will be used to design future clinical evaluation.

14.3. Analysis Populations

Safety Population:

All subjects who were administered any test article excluding subjects who drop out prior to administering any test article. At least one observation should be recorded.

Per-Protocol Population:

All subjects who have successfully completed all visits and did not substantially deviate from the protocol as determined by the trial cohort review committee prior to database hard lock (Per-Protocol Population). Justification of excluding subjects with protocol deviations in the per-protocol population set will be documented in a memo to file.

Intent-to-Treat (ITT) Population:

All randomized subjects regardless of actual treatment and subsequent withdrawal from study or deviation from protocol. At least one observation should be recorded.

14.4. Level of Statistical Significance

All planned analysis for this study will be conducted with an overall type I error rate of 5%.

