2.3. Hypotheses

The test solution will be similar to the control solutions with respect to initial comfort at 1-min, 5-min, 45-min and 2 hours post-fit of pre-soaked lenses.

This is a pilot study and all the hypothesis are exploratory in nature.

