14.5. Primary Analysis

Initial comfort scores at 1-min, 5-min, 45-min and 2-hour post-fit will be analyzed using a multivariate hierarchical Bayesian model for repeated measures to test for the difference between the test solution and control solutions at 1-min, 5-min, 45-min and 120-min. The regression model will include sequence, period, solution, lens and lens by solution interaction as fixed effects. Investigational site, subjects and eye nested within subjects will be included as random effect factors.

The Model:

Let $\mathbf{y}_{ijk} = (y_{1ijk}, y_{2ijk}, y_{3ijk}, y_{4ijk})$ denote the initial comfort scores for the i^{th} eye of the j^{th} subject, from k^{th} site at 1-min, 5-min, 45-min and 2-hour post fit. The likelihood of \mathbf{y}_{ijk} is constructed as follow:

$$\mathbf{y}_{ijk} \sim N(\boldsymbol{\mu}, \boldsymbol{\Sigma}),$$

where $\boldsymbol{\mu} = (\mu_1, \mu_2, \mu_3, \mu_4)^T$ and $\boldsymbol{\Sigma}$ is a 4×4 variance-covariance matrix. Here μ_1, μ_2, μ_3 and μ_4 are given by:

$$\mu_i = \mu_0 + \beta_1 \text{sequence} + \beta_2 \text{period} + \beta_3 \text{lens} + \beta_4 \text{solution} + \beta_5 \text{lens*solution} + \delta_{i(jk)} + \delta_{j(k)} + \delta_k,$$

where $\delta_{i(jk)} \sim N(0, \sigma_{\text{eye}}^2)$, $\delta_{j(k)} \sim N(0, \sigma_{\text{subj}}^2)$, $\delta_k \sim N(0, \sigma_{\text{site}}^2)$. Other baseline characteristics such as age, gender and CLDEQ-8 score will also be included as fixed effects when appropriate.

Non-informative prior distributions will be used for the coefficients in the models as well as for the error terms: Independent vague normal $N(0, 1000)$ priors for the regression coefficients (μ_0 and $\boldsymbol{\beta}$), inverse gamma $IG(0.001, 0.001)$ for $\sigma_{\text{eye}}^2, \sigma_{\text{subj}}^2, \sigma_{\text{site}}^2$ and inverse Wishart $IW(R, 4)$ for $\boldsymbol{\Sigma}$. R is determined by $S = E[\boldsymbol{\Sigma}] = 4R$ where S is the sample variance-covariance matrix of the \mathbf{y}_{ijk} . The Metropolis sampler algorithm as implemented in the MCMC Procedure (SAS 9.4, SAS Institute, Cary, NC) will be used to estimate the posterior distributions of the unknown parameters. Inferences will be made based on a posterior credible interval for the relevant parameters. Results will be reported as regression coefficient mean estimates with 95% credible intervals.

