14.6. Secondary Analysis

Not applicable.

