14.7. Other Exploratory Analyses

Further exploratory analysis will be conducted on corneal staining, subjects reported ocular symptoms and ocular adverse events at the discretion of the Study Responsible Clinician.

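### Section 14.4 claims an overall 5% type I error rate, but the plan tests two controls at four times with 95% intervals and states nothing that would hold the rate at 5%

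*Combined protocol and SAP*

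**What the plan says.** Section 14.4 (Level of Statistical Significance) is one sentence: "All planned analysis for this study will be conducted with an overall type I error rate of 5" percent. It makes no exception for exploratory work.

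Section 14.5 (Primary Analysis) fits a Bayesian repeated-measures model "to test for the difference between the test solution and control solutions at 1-min, 5-min, 45-min and 120-min". Section 2.1 names two controls, CLEAR CARE and OPTI-FREE PureMoist. The basis for inference is: "Inferences will be made based on a posterior credible interval for the relevant parameters". No level is given in that sentence. The only level in the plan is in the reporting sentence: "Results will be reported as regression coefficient mean estimates with 95% credible intervals".

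On what else might fall under the claim:
- Section 14.1: "Summaries will be presented by study solution, by lens type and across all lens types".
- Section 14.6 (Secondary Analysis): "Not applicable".
- Section 14.7: "Further exploratory analysis will be conducted on corneal staining, subjects reported ocular symptoms and ocular adverse events at the discretion" of a sponsor clinician.
- Section 14.8 plans no interim analysis.

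Section 2.3 sets the status of the hypotheses: "This is a pilot study and all the hypothesis are exploratory in nature". Section 14.2 adds that the sample size has no power calculation behind it and that the data will inform a later study.

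**The concern.** A 95% interval read as a test gives a 5% error rate for one contrast. For the rate to be 5% overall, either there must be only one contrast or something must link the contrasts: an adjusted level, a testing order, a single main time and control, a simultaneous interval, or a rule that all must pass. None of these appears in 14.1 to 14.10, and the Bayesian rule is not calibrated to a frequentist error rate.

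The size of the family is also unclear. The text of 14.5 implies eight contrasts (two controls by four times). The printed mean equation has no time-specific coefficients, so read literally it gives one solution effect per control: two contrasts averaged over lenses, or six if taken by lens through the interaction term. If the section 14.7 analyses count as planned, the family has no fixed size.

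At stake is how the result is read. A report could show a difference at one time against one control beside a claim of 5% overall error, and whoever designs the next study would trust it too far. The error meant here is a false difference, which is the error of the test in 14.5. It is not the error of concluding similarity, where a false difference errs in the opposite direction.

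**Working it through.** **Inputs.** Claimed overall rate 5% (14.4). Interval level 95% (14.5). Four times (14.5). Two controls (2.1). Three lens types with a lens-by-solution term (14.5). Sidedness is not stated; two-sided is taken from the wording of the test. The documents give no correlations, so ranges are assumed: 0.3 to 0.9 between times and 0 to 0.5 between the two control contrasts. No standard deviation is needed.

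**Assumption.** With priors the plan describes as non-informative, each 95% credible interval is treated as a two-sided 5% test on a normal contrast.

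**Step 1: reproduce the plan's figure.** With one contrast, 1 − 0.95 = 5.0%. This is the only case that gives 5%, and the plan names no single contrast.

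**Step 2: independent contrasts**, 1 − 0.95^k:

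| Reading | k | Chance of at least one false difference |
|---|---|---|
| Two controls, literal equation, across lenses | 2 | 9.75% |
| Two controls × three lenses, literal equation | 6 | 26.5% |
| Two controls × four times, text of 14.5 | 8 | 33.7% |
| Two controls × four times × three lenses | 24 | 70.8% |

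**Step 3: correlation between the two control contrasts.** Both share the test solution. If the test mean pools both periods with independent residuals, each difference has variance 1 + 0.5 = 1.5 and the covariance is 0.5, so the correlation is 0.5/1.5 = 1/3. For two bivariate normal contrasts the rate p₂ is 9.75%, 9.46% and 9.07% at correlation 0, 1/3 and 0.5. These are also the limits for the eight contrasts when the four times are perfectly correlated.

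Lens types are worn by different subjects, so the lens-specific sets are taken as independent. For six contrasts, 1 − (1 − p₂)³ gives 26.5%, 25.8% and 24.8%.

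**Step 4: eight correlated contrasts.** The correlation matrix is (control) ⊗ (time), with equal correlation between times. Results are from simulation, with numerical integration as a check where the control correlation is 0:

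| Between-time correlation | Control correlation 0 | Control correlation 0.5 |
|---|---|---|
| 0.3 | 31.8% | 29.8% |
| 0.5 | 28.7% | 26.9% |
| 0.7 | 24.4% | 22.7% |
| 0.9 | 17.8% | 16.5% |
| 1.0 (limit) | 9.75% | 9.1% |

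**Step 5: cost of keeping 5% overall.** The 95th percentile of the largest |Z| among the eight is 2.48 at correlations 0.9/0.5 (time/control), 2.72 at 0.3/0 and 2.727 under independence. Divided by 1.96, these make the intervals 27% to 39% wider. A true difference that an unadjusted interval shows 80% of the time lies at 1.96 + 0.8416 = 2.80 standard errors. With simultaneous bands it is shown Φ(2.80 − 2.48) ≈ 63% to Φ(2.80 − 2.727) ≈ 53% of the time.

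**The case against.** The strongest reply is that nothing depends on the sentence. The study is a pilot, its hypotheses are exploratory, there is no margin or decision rule, and unadjusted intervals are acceptable in such a setting. That stands and limits the weight. It does not rescue 14.4: an exploratory study needs no overall error guarantee, which is a reason not to claim one.

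A second reply is that section 14.5 never calls its intervals unadjusted and gives no level in the inference sentence, so 14.4 might be read as setting the rate those intervals must meet. It is true that the lack of adjustment is inferred from silence. But on that reading the plan still has no method for reaching 5%.

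Third, the percentages come from idealised normal contrasts with assumed correlations, not from a simulation of the printed model. That also stands, and the individual figures should not be quoted as properties of this plan. The direction is secure: with two controls, every case computed is about 9% or more.

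Fourth, the summaries in 14.1 are descriptive, and analyses chosen at a clinician's discretion are hard to call planned. Both points are fair. Doubt about the level of testing comes mainly from the lens-by-solution term, and the figures above count no 14.7 analysis.

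Finally, a similarity rule requiring every contrast to pass would need no adjustment. The plan states neither that rule nor a margin, and 14.5 tests for a difference.

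**Conclusion.** The concern holds. Section 14.4 asserts an overall 5% rate that nothing else in the plan delivers. Under the text of 14.5 the rate of at least one false difference is about 16.5% to 31.8% over the assumed correlations, and 33.7% if the contrasts are independent. The most lenient reading, with two contrasts or perfectly correlated times, gives 9.1% to 9.75%. Testing by lens raises it to 24.8% to 26.5% for six contrasts, or 70.8% for 24 independent ones.

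The figures rest on treating each credible interval as a two-sided 5% test and on the stated correlation ranges. The conclusion does not depend on where in those ranges the truth lies. The sentence should be corrected; because the study is an exploratory pilot, the defect is an inaccurate statement rather than a threat to a confirmatory result.

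**What to change.** **Preferred.** Replace section 14.4 with: *Each 95% credible interval is unadjusted and exploratory; no overall error rate is claimed.* This is one sentence, with no new data or modelling. It also removes the implied guarantee for the 14.7 analyses. The 95% level remains in 14.5.

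**Optional, only if the sponsor wants to keep an overall 5%.** Define the eight across-lens contrasts as the family, rewrite the model equation with a solution effect at each time, report simultaneous 95% bands from the MCMC draws (max-|t|), and label the lens-specific contrasts and the 14.7 analyses as descriptive. Besides the new equation, the cost is the loss of detection in Step 5: true differences that unadjusted intervals would miss 20% of the time would be missed 37% to 47% of the time.

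**Secondary, and not part of the weight given to this point.** Section 2.3 expects similarity while 14.5 tests for a difference without a margin, so the plan does not say how similarity would be concluded. Add to 2.3: *An interval containing zero will not be taken as evidence of similarity.*

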14.5. Primary Analysis

Initial comfort scores at 1-min, 5-min, 45-min and 2-hour post-fit will be analyzed using a multivariate hierarchical Bayesian model for repeated measures to test for the difference between the test solution and control solutions at 1-min, 5-min, 45-min and 120-min. The regression model will include sequence, period, solution, lens and lens by solution interaction as fixed effects. Investigational site, subjects and eye nested within subjects will be included as random effect factors.

The Model:

Let $\mathbf{y}_{ijk} = (y_{1ijk}, y_{2ijk}, y_{3ijk}, y_{4ijk})$ denote the initial comfort scores for the i^{th} eye of the j^{th} subject, from k^{th} site at 1-min, 5-min, 45-min and 2-hour post fit. The likelihood of \mathbf{y}_{ijk} is constructed as follow:

$$\mathbf{y}_{ijk} \sim N(\boldsymbol{\mu}, \boldsymbol{\Sigma}),$$

where $\boldsymbol{\mu} = (\mu_1, \mu_2, \mu_3, \mu_4)^T$ and $\boldsymbol{\Sigma}$ is a 4×4 variance-covariance matrix. Here μ_1, μ_2, μ_3 and μ_4 are given by:

$$\mu_i = \mu_0 + \beta_1 \text{sequence} + \beta_2 \text{period} + \beta_3 \text{lens} + \beta_4 \text{solution} + \beta_5 \text{lens*solution} + \delta_{i(jk)} + \delta_{j(k)} + \delta_k,$$

where $\delta_{i(jk)} \sim N(0, \sigma_{\text{eye}}^2)$, $\delta_{j(k)} \sim N(0, \sigma_{\text{subj}}^2)$, $\delta_k \sim N(0, \sigma_{\text{site}}^2)$. Other baseline characteristics such as age, gender and CLDEQ-8 score will also be included as fixed effects when appropriate.

Non-informative prior distributions will be used for the coefficients in the models as well as for the error terms: Independent vague normal $N(0, 1000)$ priors for the regression coefficients (μ_0 and $\boldsymbol{\beta}$), inverse gamma $IG(0.001, 0.001)$ for $\sigma_{\text{eye}}^2, \sigma_{\text{subj}}^2, \sigma_{\text{site}}^2$ and inverse Wishart $IW(R, 4)$ for $\boldsymbol{\Sigma}$. R is determined by $S = E[\boldsymbol{\Sigma}] = 4R$ where S is the sample variance-covariance matrix of the \mathbf{y}_{ijk} . The Metropolis sampler algorithm as implemented in the MCMC Procedure (SAS 9.4, SAS Institute, Cary, NC) will be used to estimate the posterior distributions of the unknown parameters. Inferences will be made based on a posterior credible interval for the relevant parameters. Results will be reported as regression coefficient mean estimates with 95% credible intervals.

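### Section 14.5 promises test-control differences at four times, but its model has no time-specific coefficient and so forces the same difference at all four

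*Combined protocol and SAP*

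**What the plan says.** The target is time-specific throughout. Section 2.3 expects the test solution to be "similar to the control solutions with respect to initial comfort at 1-min, 5-min, 45-min and 2 hours post-fit", sections 2.1 and 2.2 name the same four times, and section 14.5 gives the purpose of the primary model as "to test for the difference between the test solution and control solutions at 1-min, 5-min, 45-min and 120-min".

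The model in section 14.5 is described in three places:

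- The list of terms: "The regression model will include sequence, period, solution, lens and lens by solution interaction as fixed effects". Site, subject and eye within subject are random effects. Only baseline characteristics (age, gender and CLDEQ-8 score are the examples) may be added.
- The equation. The response vectors "denote the initial comfort scores for the i^{th} eye of the j^{th} subject, from k^{th} site at 1-min, 5-min, 45-min and 2-hour post fit" and are normal with means mu_1 to mu_4 and a 4 x 4 covariance matrix Sigma. One line then defines mu_i from mu_0, beta_1 to beta_5 and the random effects. None of these carries a time index.
- The priors. They are given for one mu_0 and one vector beta.

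On output, the section says "Results will be reported as regression coefficient mean estimates with 95% credible intervals". Section 14.6 plans no secondary analysis. Section 14.7 says "Further exploratory analysis will be conducted on corneal staining, subjects reported ocular symptoms and ocular adverse events", which does not include comfort. Section 14.1 plans descriptive summaries by solution and lens type. Section 14.2 says of the pilot: "The collected data will be used to design future clinical evaluation".

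**The concern.** The list, the equation and the prior statement agree with each other and disagree with the purpose of the model. If no coefficient varies with time, the solution effect cannot vary with time either, so there is one answer where four are promised. Mean comfort within a cell is also held flat from 1 minute to 2 hours. Sigma lets variances and correlations differ by time, but not means.

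The notation does not help a programmer recover the intent. The subscript i is the eye in the response and in the eye random effect, but must be the time point in mu_i.

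Comfort just after inserting a soaked lens may well differ from comfort two hours later. Under the written model, an early difference that fades would be understated at 1 minute and carried over to 2 hours. A difference that reverses could vanish altogether.

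**Working it through.** The plan gives no power figure, SD or correlation, so there is no figure of its own to reproduce. The check has a structural part, which needs no assumptions about the data, and an illustration, which does.

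**1. Parameters and contrasts.** Inputs: three lenses, two sequences and two periods (section 5.1), a three-level solution factor, and four times.

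- As written: 1 intercept + 1 sequence + 1 period + 2 lens + 2 solution + 4 lens-by-solution = 11 mean parameters.
- Every coefficient indexed by time: 4 x 11 = 44. The design matrix has rank 44, so all are estimable.
- Test-control differences as written: 3 lenses x 2 controls = 6, each the same combination of beta_4 and beta_5 at every time. The stated question needs 6 x 4 = 24, and the indexed model supplies 24.

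**2. What the single difference estimates.** Assume between-eye differences with equal variance at the four times and AR(1) correlation rho. Generalised least squares for a common difference gives (1'R^-1 d)/(1'R^-1 1). Under AR(1) the weights are proportional to 1, 1-rho, 1-rho, 1, with sum 4-2rho.

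| True differences d (assumed) | rho = 0.5 | rho = 0.8 |
|---|---|---|
| -8, -5, -2, 0 | (-8 - 2.5 - 1)/3 = -3.83 | (-8 - 1 - 0.4)/2.4 = -3.92 |
| -10, -5, 0, 0 | (-10 - 2.5)/3 = -4.17 | (-10 - 1)/2.4 = -4.58 |
| -6, -2, 2, 6 | 0.00 | 0.00 |

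**3. Precision.** The variance ratio of a time-specific to the common difference is 1'R^-1 1 = (4-2rho)/(1+rho). For rho = 0.5 this is 3/1.5 = 2, an SE ratio of 1.414. For rho = 0.8 it is 2.4/1.8 = 1.333, an SE ratio of 1.155. With an assumed SD of 15:

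- n = 30 (one lens): time-specific SE 15/sqrt(30) = 2.74, against 1.94 to 2.37 for the common difference.
- n = 90 (all lenses): 15/sqrt(90) = 1.58, against 1.12 to 1.37.

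**4. Coverage.** A simulation drew four-variate normal between-eye differences with true values -8, -5, -2, 0. It fitted a common difference by maximum likelihood with unstructured covariance and no priors, with 2,000 replicates per case. At SD 15, the nominal 95% interval covered the true value as follows:

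| | 1 minute | 2 hours |
|---|---|---|
| n = 30 | 37-54% | 45-54% |
| n = 90 | 5-19% | 9-21% |

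The ranges run over rho 0.5 to 0.8. Letting the SD vary from 10 to 20 widens the n = 30 ranges to 12-67% and 18-67%.

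**5. The opposite case.** If the true difference is constant over time, the written model is unbiased and more precise, by the SE ratios in step 3.

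**The case against.** The strongest reply is that this reads shorthand too literally. In a multivariate regression, time is the response dimension and not a covariate, so its absence from the list of effects is expected. One generic row is often written for component-specific coefficients, and four named means would serve no purpose if they were equal. This makes a time-specific intention plausible. It does not make the text correct: the list, the equation and the prior statement would all need amending to say so.

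A second reply is that the summaries in section 14.1 should show comfort by solution and lens. That mitigates the problem, but the section does not say by time and promises no test-control contrasts or intervals.

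Third, the illustration is not the planned analysis. Effect profile, SD and correlation are assumed. Table 5 gives seven comfort scores per eye per period (1, 5 and 45 minutes at the first visit; 1, 5, 45 and 120 minutes at the second), not one set of four. RevitaLens is worn in both periods, and the planned model has eye and subject random effects. These points stand against reading the SEs and coverage figures as forecasts. They do not affect the structural result or the direction of the bias.

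Fourth, this is a pilot with exploratory hypotheses and no power calculation. That limits the severity.

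**Conclusion.** The concern holds. As written, the primary model gives one test-control difference per lens and control, so it cannot deliver the differences at four times that sections 2.3 and 14.5 call for. The count of 6 against 24 rests only on the printed model and a three-level solution factor.

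The size of the error depends on how far the true difference changes over the two hours. For an assumed fading difference of -8 to 0, the single estimate is about half the 1-minute value and about 4 points off at 2 hours. For a constant difference there is no error. No confirmatory claim is at stake, but this is the only modelled analysis of comfort and its estimates are to inform later studies. It should be corrected before the database is locked, so that the choice of model does not follow the data.

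**What to change.** In section 14.5, give the mean at time t its own intercept and coefficients:

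mu_t = mu_0t + beta_1t sequence + beta_2t period + beta_3t lens + beta_4t solution + beta_5t lens*solution + the random effects.

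State the priors for the time-indexed set, and use different subscripts for time and eye. A smaller model, not equivalent, adds time, solution*time, lens*time and lens*solution*time. It has 9 lens-solution cells x 4 times + sequence + period = 38 mean parameters, and holds sequence and period effects constant over time.

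Report posterior contrasts of test minus OPTI-FREE and test minus CLEAR CARE at each time, by lens and averaged over lenses. The factor coding is not stated, and contrasts do not depend on it. The same revision should say how the repeated 1-, 5- and 45-minute scores within a period enter the model, since indexing by time does not settle that.

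The cost is SAP wording and a few lines of PROC MCMC code, with no new data. There are more parameters, and each time-specific interval is about 1.15 (rho = 0.8) to 1.41 (rho = 0.5) times as wide as the single-effect interval under the assumptions above.
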